4.1 Dispositions of Subjects and Analysis Sets

Disposition of patients and study discontinuation

The disposition of patients, patients per center, inclusion and exclusion criteria, the status of study completion / study discontinuation and survival (telephone contact) as well as the number and percentages of patients discharged from hospital by visit will be shown.

4.2 Demographics and Other Covariates

Demographic data

Demographic data (Age, Age group (< 65 years/ >= 65 years), Sex, Race, Ethnicity, Body weight, Body height, BMI (Body Mass Index)) will be tabulated and listed.

Other demographic data like history of smoking and alcohol use, if available, will be listed only.

Prior and concomitant medication (CM)

Prior and concomitant medications will be coded by WHO-DD valid version at the end of the study.

Concomitant medications are defined as all medications with stop date >= date of first study medication or ongoing if started before date of first study treatment.

Prior medications include all medications that started and stopped before the date of first study medication. Medications with insufficient date information to determine whether or not they were concomitant will be considered concomitant.

Concomitant medication will be tabulated by anatomical therapeutic chemical (ATC) level 1, ATC level 4, preferred name and listed as well. Prior medication will be listed only.

Comorbidity

Number and percentage of patients with at least one comorbidity (arterial hypertension, diabetes and coronary artery disease) will be shown.

All comorbidity data will be listed as well.

Medical history (MH)

MH events will be tabulated by system organ class and current treatment status (currently treated/ currently not treated). The number of events, as well as the number and rate of affected patients will be reported for each treatment group.

All medical history data will be listed as well.

Respiratory condition (arterial blood gas analysis or pulse oximetry)

Arterial blood pH, PaO₂ and PaCO₂ will be presented using basic statistics of absolute values for all visits and change from baseline for all post-baseline visits.

All respiratory data will be listed as well.

Pregnancy test

The proportion positive or negative pregnancy test results will be tabulated by visit for females with childbearing potential.

All pregnancy test data will be listed as well.

Physical examinations (PEs)

The frequencies of changes (Evaluation (Normal / Abnormal – CS / Abnormal – Not CS)) in PEs (all body systems) since baseline will be shown for all visits using shift tables.

All physical examination data will be listed as well.

Patient status assessment

Patient status assessment will be presented using frequency tables.

Patient status assessment data will be listed as well.

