8 INVESTIGATIONAL PLAN

8.1 Overall Study Design and Plan-Description

The clinical trial is designed as a prospective, multi-centre, double-blind, randomized, placebo-controlled, interventional trial to assess clinical safety, tolerability, and efficacy of APN01 on top of best standard of care (SOC) in patients with severe COVID-19 and to evaluate if treatment with APN01 on top of SOC is superior to placebo (NaCl 0.9%) on top of SOC.

SOC treatment (such as Concomitant medication, remdesivir (if approved and available) and ventilation techniques) will be documented in the eCRF and considered for evaluation for study data. SOC treatment follows the national guidelines (<https://www.ersnet.org/covid-19-guidelines-and-recommendations-directory>).

The study will comprise two treatment groups as follows:

- Group A (active): APN01 (5 mg/ml, 4 ml/vial)
- Group B (placebo control): sterile, 0.9% sodium chloride

Eligible patients are centrally allocated using a dynamic randomization (1:1) to Group A or B to receive the treatment or placebo. Dynamic randomization factors will be age in years (continuous) and center. The entire study team will be blinded except for an unblinded pharmacist or an unblinded study team member (including team members involved in the IMP preparation, unblinded statisticians and DSMB members involved in DSMB, unblinded data managers involved in generation and the upload of treatment listings to eCRF). . Randomization will be carried out centrally using the electronic case report form (eCRF).

After screening at day -1 and randomization at day -1 or 1, the patients will be treated with APN01 or Placebo intravenously twice daily (BID) every 12 hours (\pm 1 hour) over 3 to 30 minutes in the morning and the evening until day 7. Preparation of APN01 (0.4mg/kg BID for seven calendar days) and placebo (normal saline) will be carried out according to the Pharmacy Manual. The IMP will be administered in a double-blind manner (investigators, study team and patients will be blinded to the treatment administered).

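### Read literally, SAP 4.2 puts drugs started on or after first dose and still ongoing in neither the concomitant nor the prior class

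*SAP*

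**What the plan says.** SAP section 4.2, under prior and concomitant medication, defines the concomitant class as "all medications with stop date >= date of first study medication or ongoing if started before date of first study treatment". That gives two routes into the class. The first is by stop date, on or after first dose. The second is for drugs without a stop, and it asks for a start before first dose.

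The other class is defined as follows: "Prior medications include all medications that started and stopped before the date of first study medication". A fallback then says: "Medications with insufficient date information to determine whether or not they were concomitant will be considered concomitant".

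The outputs depend on the class. "Concomitant medication will be tabulated by anatomical therapeutic chemical (ATC) level 1, ATC level 4, preferred name and listed as well", whereas "Prior medication will be listed only". No output is described for a drug in neither class.

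On the data side, protocol section 8.4.7 requires any treatment given during the study to be entered in the eCRF with its start and stop dates. Protocol section 8.1 says that standard-of-care treatment, with remdesivir among the examples, "will be documented in the eCRF and considered for evaluation for study data".

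**The concern.** The ongoing route carries a start-date condition that the rule does not need. It admits a drug that was running before the first dose and never stopped, but says nothing of a drug begun during the trial and never stopped. In hospitalised patients followed to Day 28, treatment begun after randomisation and still running at last contact is an ordinary pattern. It is also part of the background treatment that a reader would want to compare between the arms.

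What is at stake is the completeness of one descriptive table and its listing. The data themselves would still be in the eCRF.

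**Working it through.** The plan attaches no figure to this rule, so there is none to reproduce. The check is to write the rule out and pass each possible record through it.

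**Inputs, all from SAP 4.2.** Let T0 be the date of first study medication, set to Day 1.

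- C1 (concomitant by stop date): a stop date is recorded and stop ≥ T0.
- C2 (concomitant by ongoing status): flagged ongoing and start < T0.
- P (prior): start < T0 and stop < T0.
- F (fallback to concomitant): the dates are insufficient to decide. This is taken strictly, as a missing stop date without an ongoing flag, or an ongoing flag with an unknown start.

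**Results under the rule as written.**

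| Start | Stop | C1 | C2 | P | F | Class |
|---|---|---|---|---|---|---|
| Day -10 | Day -2 | no | no | yes | no | prior |
| Day -10 | Day 5 | yes | no | no | no | concomitant |
| Day -10 | ongoing | no | yes | no | no | concomitant |
| Day 3 | Day 9 | yes | no | no | no | concomitant |
| Day 1 | ongoing | no | no | no | no | **neither** |
| Day 3 | ongoing | no | no | no | no | **neither** |
| unknown | ongoing | no | no | no | yes | concomitant |
| Day 3 | unknown, not flagged ongoing | no | no | no | yes | concomitant |

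Two of the eight patterns have no class. The gap includes a drug started on the day of first dose itself. The last two rows show an oddity: a drug with poorer date information is kept, while one with a known start and a clear ongoing flag is not.

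**Does another part of the SAP close the gap?** Three places bear on it.

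- SAP 4.7 rules out imputation of missing values, so nothing there supplies a stop date for an ongoing drug.
- SAP 4.4.2, on ventilator-free days, says how ongoing ventilation is handled: it runs to study completion, discontinuation or death. No matching sentence exists for medications.
- SAP 4.5 splits adverse events by onset before, or on or after, first dose, with a rule for incomplete dates. That scheme places every event in treated patients; the medication scheme does not do the same for drugs.

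**Could the start-date condition be meant to apply to both routes?** That reading is worse. The Day 3 to Day 9 drug would then also lose its class.

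**After the change.** Replace C2 by: flagged ongoing, with no condition on start. The Day 1 and Day 3 ongoing drugs become concomitant, the other six patterns keep their class, and each of the eight falls in exactly one class.

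**Size.** Let f be the share of drugs started on or after first dose that are still ongoing at last contact, and s the share of all truly concomitant records that started on or after first dose. The table would lose f × s of its records. The documents give neither f nor s.

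**The case against.** The best reply is that the intent is plain. A drug begun after the first dose and still running must stop, whenever it does, after the first dose, so it meets the sense of the stop-date route. The ongoing clause can then be read as settling only the doubtful case of a drug that predates dosing. The prior class is narrow and doubtful records go to concomitant, so the design seems to be that whatever is not clearly prior is concomitant. A programmer might also treat the blank stop date as insufficient date information. SAP section 5 lists no narrowing of the protocol's scope, and the table specifications are in Appendix A, which is not in the supplied text.

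Most of this stands as to intent, and it means that omission is possible rather than certain. It does not repair the wording. If ongoing status already implied a qualifying stop date, the second route would be redundant. A known start with an ongoing flag is enough information to decide, so the fallback does not clearly apply. Appendix A might settle the matter but could not be checked.

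A reader might also infer more than the documents support:

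- *That these drugs will certainly be missing from the tables.* This holds only if the rule is programmed literally.
- *That a forbidden drug started on study could escape notice.* SAP 4.8 has forbidden concomitant medication examined at the blind data review on all data, and nothing in the supplied text makes that review or per-protocol exclusion depend on this classification.
- *That treatment continued up to discharge is lost.* A drug with a recorded stop at discharge, or on any date from first dose onward, is captured by the stop-date route.
- *That a percentage of the table is lost.* No source supports one. A share of on-study starts would also not equal the share of the table, which holds drugs begun before first dose as well.

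**Conclusion.** The point holds as a drafting error with a limited consequence. As written, the rule leaves unclassified every medication that starts on or after the date of first study medication and is still flagged ongoing at last contact. A literal program would leave those records out of the concomitant table and listing.

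The conclusion rests on two assumptions: that an ongoing flag comes with no stop date, and that the fallback is not stretched to cover it. The number of records affected cannot be derived from the documents.

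No inference is touched. The logistic models in SAP 4.4 adjust for hypertension, diabetes, coronary artery disease, age and center. The LDH regression uses baseline log LDH, center and age, and the Cox models use center and age. None has a medication term, and no endpoint or analysis set is defined from the class of a drug. This is a worthwhile correction, but not one on which the trial's conclusions turn.

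**What to change.** Change one phrase in SAP 4.2 so that the definition reads, in substance: *concomitant medications are those with a stop date on or after the date of first study medication, or ongoing, whatever the start date.* Keep the prior definition and the incomplete-date fallback as they are, and confirm that the Appendix A specifications use the same rule.

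The cost is one sentence in the SAP and one condition in the program. No new data are needed, and no endpoint, test or analysis set changes.

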4.3 Study Drug Administration

IMP administration

Each patient should receive 14 doses of IMP (APN01 or Placebo). The first IMP administration will be performed after randomization at screening or at day 1. If the first IMP administration is performed at day 1 at the evening, patient will receive the 14th dose on day 8 in the morning. IMP administration at screening and at day 8 as well as all related assessments (e.g. ECG, Vital signs, etc.) are documented in eCRF as IMP administration or assessment on unscheduled visit and will be shown in TLGs as IMP administration or assessment on screening and day 8 respectively (instead of unscheduled visit, i.e. renaming of unscheduled visits in this cases).

Total study drug exposure and total study drug exposure complete will be tabulated and listed.

Therefore, the frequency tables in overall as well as by Age group (< 65 years/ >= 65 years to < 75 years/ >= 75 years to < 80 years/ >= 80 years), Sex, Race and Ethnicity will be provided.

Total study drug exposure [days] is calculated as sum of days with at least 1 administered dose (complete or not complete) of IMP (APN01 or Placebo).

Total study drug exposure complete [days] is calculated as sum of days with two complete administered doses of IMP (APN01 or Placebo).

All other IMP administration data will be listed only.

Total dose per day of study medication taken [mg] is calculated as sum of first and second administered doses of IMP (APN01 or Placebo).

Total volume per day of infusion [ml] is calculated as sum of first and second administered volume of infusion.

Total dose of study medication taken [mg] is calculated as sum of daily administered doses of IMP (APN01 or Placebo).

Total volume of infusion [ml] is calculated as sum of daily administered volume of infusion.

4.4 Efficacy Analysis

In case that the first IMP is given at night of Screening visit, the duration of the study might be 29 days as a maximum. Therefore, a time window of 27 to 29 days will be applied where applicable.

4.4.1 Analysis of Primary Efficacy Endpoint

The primary endpoint is a composite endpoint of all cause-death or invasive mechanical ventilation (up to 28 days or hospital discharge).

The following null hypothesis will be tested:

- $H_0: p_{APN01} = p_{Placebo}$

versus the alternative

- $H_1: p_{APN01} \neq p_{Placebo}$

H_0 will be tested using a Chi-squared test. The level of significance is 5% (two-sided). In addition, logistic regression analyses will be conducted considering additional co-factors.

All cause-death

The percentage of patients who have died at Day 28 will be presented by treatment group.

Patients with death from any cause will be used for this endpoint as part of responder. Patients who are still alive at Day 28 will be considered as non-event.

The following cases may occur:

- Patient discharged from hospital **and** discontinued before Day 28, will be followed up by telephone interview to check whether they are alive or dead, if unclear as no telephone interview available, death is assumed (worst case) at last available date of early termination, hospitalization or hospital discharge
- No discharge from hospital, **but** early discontinuation before Day 28 will be followed up by telephone interview to check whether they are alive or dead, if unclear as no telephone interview available, death is assumed (worst case) at date of early termination
- Discharged from hospital, **but** no discontinuation before Day 28: No telephone interview, but regular entry at Day 28 about alive/death status

Invasive mechanical ventilation (up to 28 days or hospital discharge)

Invasive mechanical ventilation is defined as patients who are intubated or have a tracheostomy tube and are receiving positive pressure ventilation. Patients with at least one invasive mechanical ventilation (event with type of ventilation 'Mechanical ventilation') up to 28 days or hospital discharge will be used for this endpoint as part of responder.

Chi-squared test

Proportion of responder, i.e. those patients that died or having an invasive mechanical ventilation (up to 28 days or hospital discharge), as well as the p-value (two-sided) will be reported.

Logistic regression

A logistic regression with the responder (yes/no) as independent variable will be applied.

The following co-factors will be included in the logistic regression:

- Arterial hypertension

- ❑ Diabetes
- ❑ Coronary artery disease
- ❑ Age (<65 years vs. >=65 years)
- ❑ Center

The odds ratio along with its associated 95% confidence intervals will be reported.

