8.4.3 Method of Assigning Patient to Treatment Groups

Randomization will be performed based on a variance minimization algorithm (dynamic randomization). Patients will be assigned to a given treatment arm with a probability that takes in consideration the current arm assignments (8.4.8.1). Randomization will be done via the eCRF. Patients will be assigned a sequential randomization number by the eCRF.

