8.7.2 Determination of Sample Size

186 patients (93 per group) will yield 80% power to detect a 20% absolute risk reduction in the primary composite endpoint, from 50% in the placebo group to 30% in the APN01 group at a two-sided alpha of 0.05 when applying a two group Chi-Squares test. To consider patients who will be randomized but not treated a total of 200 patients (100 per group) will be enrolled.

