4.4.2 Analysis of Secondary Efficacy Endpoints

Log transformed levels of lactate dehydrogenase (LDH) at Day 5 as a surrogate marker for organ damage (powered secondary endpoint)

Results of LDH will be converted to standard unit before any calculation if needed. Conversion of all lab values will be described in a separate document 'Conversion_3570_VX-X_2020-MM-DD'. Standardized results will be log transformed for this endpoint.

Log transformed levels of LDH will be analyzed using linear regression adjusted for baseline log levels of LDH, center and age. 95% confidence intervals will be additionally calculated.

In protocol the wording of "minimization factors" is used: Stratification factors from the randomization are used in models as covariates.

Before application of the linear regression, it will be checked if the residuals are approximately normally distributed (QQ-Plot, Shapiro Wilk test). If there are no major violations of the normal distribution the model can be applied. If there are major violations available only descriptive analyses will be displayed.

Point estimate together with standard error and two-sided 95% confidence interval as well as p-value (two-sided) will be reported.

28-day mortality (all cause death)

The percentage of patients who have died at Day 28 will be presented by treatment group.

The following cases may occur:

- Patient discharged from hospital **and** discontinued before Day 28, will be followed up by telephone interview to check whether they are alive or dead, if unclear as no telephone interview available, death is assumed (worst case) at last available date of early termination, hospitalization or hospital discharge
- No discharge from hospital, **but** early discontinuation before Day 28 will be followed up by telephone interview to check whether they are alive or dead, if unclear as no telephone interview available, death is assumed (worst case) at date of early termination
- Discharged from hospital, **but** no discontinuation before Day 28: No telephone interview, but regular entry at Day 28 about alive/death status

Chi-squared test or Fisher's exact test

Proportion of responder, i.e. those patients that died, as well as the p-value (two-sided) will be reported.

Logistic regression

The following co-factors will be included in the logistic regression:

- ❑ Arterial hypertension
- ❑ Diabetes

- ❑ Coronary artery disease
- ❑ Age (<65 years vs. >=65 years)
- ❑ Center

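### The deciding primary test is an unadjusted chi-squared although allocation is by minimisation; a covariate-adjusted test on data already collected would recover a little power at almost no cost

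*SAP*

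**What the plan says.** Both documents test equality of the two event proportions without adjustment or stratification (Protocol 8.7.1.2.5 and SAP 4.4.1). In the SAP the hypothesis "will be tested using a Chi-squared test. The level of significance is 5% (two-sided"). A logistic regression with hypertension, diabetes, coronary artery disease, age group and centre is additional; its odds ratio and 95% confidence interval are reported, but it decides nothing.

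Protocol 8.4.3 describes the allocation: "Randomization will be performed based on a variance minimization algorithm (dynamic randomization"). Protocol 8.1 names the factors: "Dynamic randomization factors will be age in years (continuous) and center". SAP section 1 gives age as under 65 versus 65 and over, and adds at least one of three comorbidities for patients randomised before version 6.0. SAP section 5 declares the age coding as a change from protocol.

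In the LDH paragraph of SAP 4.4.2 the plan adds: "Stratification factors from the randomization are used in models as covariates". The LDH model and the Cox models accordingly include centre and age.

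The sample size in Protocol 8.7.2 is built on the same unadjusted test. It assumes event rates of 50% on placebo and 30% on APN01, and arrives at 93 per group for 80% power "when applying a two group Chi-Squares test".

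**The concern.** Minimisation makes the arms more alike on its factors than simple randomisation would. The chi-squared test takes no credit for this: its variance is the one that applies when those factors are left to chance. If the factors predict outcome, the standard error is somewhat too large, the true error rate drifts below 5%, and a real effect is missed slightly more often than it need be.

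The protocol's rationale (6.1) reports that age and comorbidities were associated with mortality in a large hospital cohort. Death is one of the two components of the primary endpoint, so some prognostic value is plausible. At stake is sensitivity of the one confirmatory test, in a trial of 200 patients.

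**Working it through.** **1. The plan's own figure.** Inputs from Protocol 8.7.2: 50% versus 30%, two-sided 5%, 80% power, two-group chi-squared. With pooled variance and no continuity correction,

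n per group = [1.960 × √(2 × 0.40 × 0.60) + 0.842 × √(0.50 × 0.50 + 0.30 × 0.70)]² / 0.20²
= [1.960 × √0.48 + 0.842 × √0.46]² / 0.04 = 93.0.

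The 93 per group reproduces. At 100 per group the same formula gives Φ[(0.20 × √100 − 1.960 × √0.48) / √0.46] = 82.8%.

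**2. Simulation with age as two groups.** 200 patients, 12,000 trials per setting, null rate 50% in both arms, alternative 50% versus 30%. Not in the documents, and therefore assumed: a 0.8 probability for the favoured arm, 50% prevalence of each binary factor, 10 or 40 equal centres, comorbidity in the minimisation for the first half of patients, and all prognostic strengths. The adjusted test is logistic regression on treatment, age group and comorbidity. Results are for 10 / 40 centres.

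| Age OR, comorbidity OR, centre SD | Chi-squared size, % | Chi-squared power, % | Adjusted power, % |
|---|---|---|---|
| 1, 1, 0 | 5.4 / 5.7 | 83.4 / 83.0 | 83.2 / 82.9 |
| 1.5, 1.25, 0.25 | 5.2 / 5.2 | 83.7 / 83.5 | 83.6 / 83.5 |
| 2.5, 1.5, 0.5 | 4.7 / 4.8 | 84.4 / 83.7 | 85.4 / 84.5 |
| 4, 2.5, 0.75 | 3.3 / 3.6 | 85.9 / 85.2 | 88.3 / 87.5 |

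Monte Carlo standard error is about 0.2 points for size and 0.3 for power. The gain runs from nothing to about 2.5 points.

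**3. Simulation with age in years.** 40 centres, 8,000 trials per setting, minimisation on age group, centre and (first half) comorbidity; further assumptions are an age SD of 13 years and 50% comorbidity prevalence. The adjusted test is the standardised risk difference from a logistic model with age in years and comorbidity.

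| Age OR per decade, comorbidity OR, centre SD | Size, chi-squared / adjusted, % | Power, chi-squared / adjusted, % | Gain, points |
|---|---|---|---|
| 1, 1, 0.3 | 5.0 / 5.2 | 83.1 / 83.2 | 0.1 |
| 1.5, 1.3, 0.3 | 4.6 / 5.0 | 83.7 / 85.3 | 1.6 |
| 1.8, 1.5, 0.5 | 4.0 / 4.6 | 84.5 / 87.0 | 2.5 |
| 2.2, 1.8, 0.5 | 3.7 / 4.8 | 84.9 / 89.3 | 4.4 |

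Simulation error is about 0.25 points for size and 0.4 for power.

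**4. How much is due to minimisation?** In a further 5,000 runs per setting (assumed age mean 60, SD 12, capped at 80), the gain from adjustment in the three prognostic settings of step 3 was 1.3, 3.0 and 4.5 points under minimisation and 1.9, 3.2 and 5.3 under simple randomisation. With age as under 65 versus 65 and over, the gains under minimisation fell to 1.0, 1.5 and 2.4. The power gain therefore does not depend on minimisation; only the drop in size does.

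**5. Centre terms.** Adding 40 centre indicators to the model of step 2 raised type I error to 7.5–7.9%. That null has a 50% rate, so about 0.50 × 200 = 100 events; the design assumption of 40% overall gives only about 0.40 × 200 = 80. With 10 centre indicators type I error was 5.4–5.8%.

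**The case against.** The strongest reply is that nothing here is an error. The chi-squared test is the protocol's test and the one the sample size was computed for. The stated 80% is met exactly at 93 per group, and simulated power with 200 patients under minimisation was never below 83.0%. A mildly conservative test does not undermine a positive result. All of this stands.

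Four stronger readings are tempting and should be set aside.

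- A reader might infer that the test is conservative outright. It is so only if the factors are prognostic. With weak factors step 2 gives 5.2%, and the documents offer no effect size for the composite and no evidence of a centre effect.
- A reader might infer that minimisation bought power that the test then throws away. Step 4 shows a gain at least as large under simple randomisation.
- A reader might infer that the SAP breaks its own rule about randomisation factors. That sentence sits in the LDH paragraph and concerns models. A chi-squared test is not a model, and the primary endpoint's logistic model does include age and centre.
- A reader might conclude that the existing logistic model should simply be made decisive. With about 40 planned sites as separate terms, step 5 shows that this could inflate the error rate.

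It is also fair to say that a change of test departs from the protocol and, with age in years, reverses a coding that the SAP declares. That calls for an explicit record; it does not remove the benefit.

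**Conclusion.** The point holds as an efficiency matter. The deciding test ignores baseline information that the trial collects and, for age, balances on throughout. Under the assumed prognostic strengths and the assumed 0.8 biased coin, the chi-squared test's size is about 3.5% to 5%. Adjustment gains about 0 to 4.5 points of power with age in years, and about 0 to 2.5 with the SAP's two age groups. The upper end needs an age odds ratio of about 2.2 per decade, which the documents neither support nor exclude. If the factors carry no information, the adjusted test costs essentially nothing: 83.2% against 83.1% in step 3.

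The documents do not support calling the planned test invalid or the trial underpowered. This is a free improvement, not a required correction.

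**What to change.** Before unblinding, amend SAP 4.4.1 so that the primary two-sided 5% test is the treatment risk difference standardised from a logistic model with treatment, age and presence of at least one comorbidity. Age is best entered in years, as Protocol 8.1 has it. SAP 4.2 already plans to tabulate age and the presence of at least one comorbidity.

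Leave out individual centre terms. If centre is to be represented, pool sites, for example by country, and fix the pooling before unblinding.

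Keep the chi-squared test as a sensitivity analysis. Enter in SAP section 5 both the departure from the protocol's primary test and the age coding used. The sample-size statement can stay as it is.

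The cost is a rewritten paragraph in SAP 4.4.1, the section 5 entries and a few lines of code. No new data are needed.
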